Protocol Title:

Comparison of colon adenoma detection rate using two distal colonoscope attachments.

NCT ID: NCT02665741

Protocol Date: 8 March 2016

Author of Protocol:

[name], [name], [name], [name], [name]

UC Davis Researcher - Yes

Researcher from other institution

Private Sponsor

Cooperative Group

Other: _____

IRB Review History

N/A

Objectives

The goal of our study is to compare the effect of two different distal colonoscopy attachments on:

- (i) Adenoma detection rate
- (ii) Right sided adenoma detection rate
- (iii) Sessile serrate adenoma detection rate
- (iv) Terminal ileum intubation rate

Background

Although mortality from colon cancer is decreasing, it remains the second leading cause of cancer related death in the United States ¹. There are multiple factors contributing to this decrease, such as increased awareness, improving screening techniques, etc.

Of the available modalities approved for colon cancer screening in the United States, colonoscopy is considered the gold standard. Colonoscopy has the advantage of being both diagnostic and therapeutic, allowing the removal of pre-cancerous polyps, before the polyps can transform into cancer. Colonic polyps can occur at any location from the rectum to the cecum. Colonoscopy has been shown to be more effective in decreasing incidence of cancer in the left colon but remains limited in the detection of right sided polyps /lesions ². This difference based on location is thought to be due to several reasons. Typically the right side of the colon is less clean than the left side during colonoscopy, thereby impairing visualization of polyps. This problem has been overcome by incorporating a “split bowel preparation”, which has not become standard of care. However, the problem of not being able to visualize polyps behind folds seen in the colon persists despite improvements in the quality of cleansing of the colon. Various endoscopic technologies have been introduced with the goal of assisting with the manipulation of such colonic folds, and thereby reducing chances of missing polyps behind fold. Two such colonoscope assisted devices including the distal transparent cap , and the Endocuff device.

The Endocuff overtube is a small device with flexible arms arranged in 2 rows. Each row has 8 short, soft arms projecting away from the device. These arms are used to peel back the colonic

folds without causing physical damage to enable visualization behind colonic folds. The use of Endocuff overtube has shown promising results in terms of cecal intubation rate and time as well as adenoma detection rates ³.

The transparent cap attachment is a clear plastic device that fits at the end of the colonoscope and extends a short distance past the tip of the colonoscope. It aids in the manipulation of folds and in maintaining a suitable distance from the mucosa, with the goal of improving visualization. Although some studies comparing cap fitted colonoscopy to standard (non- attachment) colonoscopies have shown improved adenoma detection ⁴, others have shown no significant benefit ⁵.

Although, these devices have been compared with conventional colonoscopies (i.e without any distal attachment), to our knowledge, there are currently no studies that have compared these two distal colonoscope attachment devices head-to-head, and none has specifically evaluated effects on detection of right sided adenomas. Also, here at UCDavis, these devices are being used specifically in diagnostic colonoscopies for removal of large polyps and the choice of which specific device used is dependent on level of comfort of the advanced endoscopist. The endoscopists participating in our study do not currently use these devices as part of their routine colonoscopies, thus it is important to provide head to head comparison of these devices to help guide management practice.

Therefore, our goal is to compare the transparent cap fitted, Endocuff fitted and non-cap fitted (standard) colonoscopy in patients presenting to UC Davis Medical Center for screening colonoscopies.

Reference

- 1) U.S. Cancer Statistics Working Group. United states Cancer Statistics: 1999-2011. Incidence and Mortality Web based Report. Atlanta (GA): Department of Health and Human Services, Centers for Disease Control and Prevention, and National Cancer Institute; 2014.
- 2) Hermann Brenner, Michael Hoffmeister, Volker Arndt, Christa Stegmaier, Lutz Altenhofen, Ulrike Haug. Protection From Right- and Left-Sided Colorectal Neoplasms After Colonoscopy: Population-Based Study JNCI J Natl Cancer Inst (2010) 102 (2): 89-95 doi:10.1093/jnci/djp436 first published online December 30, 2009

Patients presenting to the UC Davis Medical Center Endoscopy Suites located in Folsom, Elk Grove and Sacramento for screening colonoscopy will be recruited on the day of their procedure.

Typically, these patients are either referred to UC Davis for screening colonoscopy or already being followed here.

One of our study investigators (listed on personnel sheet) will review the history of patients scheduled for their colonoscopies. Patients that meet eligibility requirements will be contacted by telephone within a week prior to their scheduled procedure (see attached telephone script). The contact information collected will be used solely for this purpose. This will provide an opportunity for the patient to have initial study information as well as sufficient time to decide on whether or not they would be interested in participating in the study. Any personal health information collected will be destroyed at the earliest opportunity.

A written information sheet (see form 502) containing important study information will be given to patient prior to or during their check in process. After adequate time has been provided to the patient to read and understand the study details, the physician performing the patient's procedure will explain the study and answer all questions pertaining to the study. Patients interested in participating will be consented.

Patients not interested in participating will proceed with their routine scheduled procedure without the use of any distal attachment on the colonoscope.

As part of the recruitment process, we would need to preview records of scheduled patients including PHI- name, medical record number and age, past medical and family histories as well as contact information. Given that this is the pre-selection review, it would be impossible to collect this information / screen for patients that meet criteria for inclusion without access to the patient information. For patients that do meet requirement for enrollment, we will be contacting them by phone to provide initial study information.

Information collected, including contact information will not be disclosed to any other persons or organization and information collected will not be re-used for any purpose outside of the study.

Compensation to the Subjects

There will be no compensation to the participants.

Study Timelines

Timeline for enrolment of subjects will be September 2015 – September 2016. This will be a one-time participation during the date of their procedure only.

Patient medical records will be accessed within 4 weeks of their colonoscopy for collection of final pathology report (adenomatous vs non adenomatous polyps). Patients will not be contacted afterwards for research purposes. They will only be contacted by their endoscopist for communication of colonoscopy results per regular standard practice at UC Davis.

Study Endpoints

Primary Endpoint

-Adenoma detection rate

Secondary Endpoints

-Proximal adenoma detection rate

-Polyp detection rate

-Cecal intubation rate

-Intubation time

-Withdrawal time

-Major complication rate (includes perforation, bleeding requiring transfusion).

Procedures Involved

Our proposed study is a randomized control trial in which patients are randomized in a single-blinded fashion into one of 3 study arms. One arm of subjects will undergo their screening colonoscopy without any colonoscope attachments (conventional). A second arm of subjects will undergo their screening colonoscopy with transparent cap attachment and a third arm will undergo their colonoscopy with the Endocuff attachment.

All methods (colonoscopy without any attachment, colonoscopy with transparent cap attachment and colonoscopy with Endocuff attachment) are approved standard of care options, and are already in clinical use.

Data that will be reviewed as part of the study includes the number of polyps, location of polyps removed, size of the polyps removed, histopathology of the polyps, and whether or not the terminal ileum was intubated if necessary. These are data points that are routinely collected and reported as part of regular care of patients.

Each study patients will be assigned a study number, which will be de-identified. No patient identifiers will be collected as part of the study.

Data and Specimen Banking

Data collected will be saved on an encrypted, password-protected computer at UC Davis Medical Center, division of Gastroenterology office located at [name].

Data Management and Confidentiality

Data collected will be saved on an encrypted, password-protected computer at UC Davis Medical Center. The computer is stored in the GI office in PSSB building. This room is accessible by staff/ faculty members of the UC Davis Gastroenterology department. Also, each study patients will also be assigned study number, which will be de-identified. This information will only be accessible by the investigators involved in the study (listed on form 211).

The data collected will be analyzed using one way ANOVA. To detect an effect size of 20%, with a power of 0.809, we would need 42 subjects in each study arm. We therefore aimed to

enroll 48 subjects into each arm (total of 4 arms) to ensure we have enough subjects in each arm to detect an effect if present. An interim analysis to test for futility will be done after 6 months.

Provisions to Monitor the Data to Ensure the Safety of Subjects

This research does not involve more than minimal risk to the subject

Withdrawal of Subjects

Participation in the study is completely voluntary, thus patients can withdraw at any time during or after the procedure. Written consent will be obtained from all subjects. Withdrawing from the procedure has no negative implication on their colon cancer screening and subsequent clinical care.

A patient may be withdrawn from the research at the discretion of the endoscopist or PI. The PI may withdraw a subject if there is a clinical suspicion for hereditary polyposis syndrome / new case of inflammatory bowel disease (IBD) based on the colonoscopy. Also, there are scenarios where the regular colonoscope is switched to a pediatric colonoscope. This occurs in patients with altered/ post-surgical anatomy. In these cases, subjects may be withdrawn from the study.. This may be needed in patients with difficult anatomy or post-surgical anatomy preventing completion of the procedure using a standard colonoscope.

Risks to Subjects

The attachment devices proposed in our study are currently approved for use in colonoscopy. Although we will make every effort to ensure that your information remains confidential, there is the risk of loss of confidentiality

Potential Benefits to Subjects

Subjects may benefit from increased adenoma detection.

Vulnerable Populations

Vulnerable populations are not included in this study

Multi-Site Research

Only UC Davis Medical Center Endoscopy suites will be involved in this study

Community-Based Participatory Research

Not applicable

Sharing of Results with Subjects

Under current standard of practice, patients are contacted by the Endoscopist either through the phone, mail, my chart or in person during a clinic visit to discuss endoscopic and pathology results. The results of the study will not be shared with subjects until the study has been completed and all of the data has been analyzed.

Setting

Our research will take place at the University of California, Davis Medical Center outpatient Endoscopy Suites. These are located in Elk Grove, Folsom and at the main hospital here in Sacramento.

Potential subjects are patients that are presenting for outpatient screening colonoscopies.

Resources Available

The Endoscopists performing these procedures are board certified Gastroenterologists, with knowledge regarding the colonoscopes and attachment devices. They will provide potential subjects with the consent forms as well as answer any questions that they may have regarding the procedure.

There are no expected physical or emotional consequences as a result of participating in this study

Prior Approvals

Not applicable

Provisions to Protect the Privacy Interests of Subjects

The only people that will have access to subject personal information are the principal investigators during the study period. All information collected (including age, gender, number and types of polyps removed, cecum intubation time and complications of procedure) will be de-identified immediately after data collection.

Compensation for Research-Related Injury

No Compensation provided

Economic Burden to Subjects

Patients presenting for colonoscopies are typically insured and are not expected to pay for screening colonoscopies. The distal attachment device will be provided at no additional cost to the patients, thus there will be no additional economic burden to the subjects

Consent Process

Currently, the standard of practice is to obtain consent prior to a colonoscopy. Some of the patients presenting for their colonoscopy are via open access, thus no colonoscopy specific clinic appointments are done before their actual procedure.

For those choosing to participate in our study, an additional consent form will be needed. Patients that are identified as being eligible for the study will be contacted 3 weeks prior to their procedure (if possible) but no less than one week via telephone by [name] or [name] or [name]. Information regarding the procedure (including the goal of the study) will be discussed with them to provide sufficient time prior to their procedure for them to consider participating or not participating. Once the subject has been contacted by telephone and has agreed to participate, the investigators will obtain the subject's address and mail them a copy of the consent form (if they are contacted three weeks before the procedure) or obtain the

subject's email address and send them a copy of the stamped consent form via email (if they are contacted fewer than three weeks before the procedure)

On the day of the procedure, the endoscopists will discuss further with the patients about the procedures - including consent, medication/ history review as well as discussions about the risks and benefits of the procedure. This conversation typically occurs in a quiet corner/ section in the pre-op rooms about 30-60 minutes before the procedure. The written consent discussion specific to our study will also be done in this same area. There is usually adequate time prior to the procedures for the consents to be done.

Please see attached Consent form (HRP-502). Non English speakers not be included in the study due to the practical difficulty with translating the study materials and consents Patients that are unable to provide consent will not be included in their study.

HIPAA Authorization for Research

Consent will be obtained from all participants and patients not able to consent (such as cognitively impaired adults) will be excluded from the study. Children are also not included in this study

Process to Document Consent in Writing

Please see attached HRP form 502

Drugs or Devices

The attachment devices being used are approved for use during colonoscopies. No investigational devices are being used in this study.

FDA Regulation	Applicable to:		
	IND studies	IDE studies	Abbreviated IDE studies
21 CFR 11 • Electronic Records and Signatures	X	X	

21 CFR 54 • Financial Disclosure by Clinical Investigators	X	X	
21 CFR 210 • Current Good Manufacturing Practice in Manufacturing, Processing, Packing, or Holding of Drugs	X		
21 CFR 211 • Current Good Manufacturing Practice for Finished Pharmaceuticals	X		
21 CFR 312 • Investigational New Drug Application	X		
21 CFR 812 • Investigational Device Exemptions		X	X
21 CFR 820 • Quality System Regulation		X

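### Major complications are a secondary endpoint, but the plan gives no time window for them and no systematic way to find events that appear after the procedure day

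*Combined protocol and SAP*

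**What the plan says.** The secondary endpoints under Study Endpoints include "Major complication rate (includes perforation, bleeding requiring transfusion". No period is attached to this rate.

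Study Timelines describes follow-up in four statements:

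- On the length of participation: "This will be a one-time participation during the date of their procedure only".
- On research contact: none is to take place once the procedure is over.
- On the chart: "Patient medical records will be accessed within 4 weeks of their colonoscopy for collection of final pathology report (adenomatous vs non adenomatous polyps".
- On clinical contact: this is limited to the endoscopist's usual reporting of findings.

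Procedures Involved describes the study data: "Data that will be reviewed as part of the study includes the number of polyps, location of polyps removed, size of the polyps removed", followed by histology and whether the terminal ileum was intubated. Complications are not named there. They are named in Provisions to Protect the Privacy Interests of Subjects, in a list of collected items ending "cecum intubation time and complications of procedure) will be de-identified immediately after data collection". That list gives neither a window nor a source. The section on monitoring data for subject safety says only that the research is of minimal risk.

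**The concern.** Perforation and bleeding after polyp removal can become apparent after the patient has left the endoscopy suite. A complication rate is interpretable only if the reader knows how long patients were observed and by what means. Here the endpoint is named, but the timeline ends participation on the day of the procedure, and the later record access is described for another purpose.

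Two things are at stake. First, a statement that no major complications occurred might rest on little more than same-day observation without saying so. Second, if some later events are picked up incidentally while pathology is being retrieved, patients will have been observed for different lengths of time, and the rate will have no defined denominator period. Both matter in a trial of devices meant to increase detection, because a reader will look at harm alongside yield.

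**Working it through.** The plan states no figure for this endpoint, so there is none to reproduce. The check is a comparison of the text, followed by a calculation of how much one event matters.

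**1. Possible routes for finding a post-discharge event**

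| Route | What the protocol says | Finds later complications systematically? |
|---|---|---|
| Study participation | Procedure date only (Study Timelines) | No |
| Research contact | None afterwards (Study Timelines) | No |
| Record access | Within 4 weeks, for the pathology report (Study Timelines) | Not planned; by chance |
| Endoscopist's contact | Routine communication of results (Study Timelines; Sharing of Results with Subjects) | Not described as a source of study data |
| List of reviewed data | Polyp items and terminal ileum (Procedures Involved) | Complications not named |
| List of collected items | Complications named (privacy section) | No window, source or method |
| Safety monitoring section | Minimal-risk statement | No procedure described |

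No route is set up to find an event after the procedure day.

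**2. Unequal observation.** Let the look-up for patient i fall on day d_i. The protocol gives only an upper limit, d_i ≤ 28. An event on day t can be noticed at that look-up only if t ≤ d_i. Unless d_i is the same for everyone, patients are observed for different times.

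**3. Effect on the rates.** Let p be an arm's true rate and s the fraction of events captured. The expected observed rate is s × p, which is below p whenever s < 1. Between arms A and B the observed difference is s_A p_A − s_B p_B. If s_A = s_B = s, this equals s(p_A − p_B): the difference shrinks but keeps its sign. If s_A and s_B differ, it can move either way. The documents give none of these four quantities.

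**4. What one event does to the report.** Input: 48 per arm (Data Management and Confidentiality); 48 × 3 = 144 agrees with Number of Subjects. Exact (Clopper-Pearson) two-sided 95% upper limits:

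- 0/48: 1 − 0.025^(1/48) = 7.4%.
- 1/48 = 2.1%: solve (1 − p)^48 + 48p(1 − p)^47 = 0.025, giving p = 11.1%.
- 2/48 = 4.2%: the same method with the three-term sum gives 14.3%.

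Fisher's exact test between two arms of 48 gives p = 1.0 for 0 versus 1 event. For 0 versus 2 events, p = 2 × C(48,2)/C(96,2) = 2 × 1128/4560 = 0.49.

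**5. How many events might arise.** The documents give no rate. Assuming a total major complication rate of 0.1% to 1%, the expected number among 144 is 144 × 0.001 = 0.14 to 144 × 0.01 = 1.4. The chance of at least one is 1 − 0.999^144 = 13% to 1 − 0.99^144 = 76%. These cover all events, same-day or later; the later share is unknown.

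**The case against.** The strongest reply is that the protocol is silent rather than restrictive. Complications are on the list of collected items with no limit to the procedure day. The limit in Study Timelines applies to the patient's participation, not to what investigators may read in the chart; the pathology look-up shows that outcome data are gathered after participation ends. Nor does the record-access sentence say that access happens a single time or exclusively for pathology.

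This stands as far as it goes. A reader might infer that delayed events are excluded, or that the endpoint is same-day by design. The documents say neither. What they support is that no window is stated and no means of finding later events is described. A look-up range starting at day 0 would also be inference, since only the upper limit is given and a final pathology report takes time.

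A second objection is that the trial cannot compare rare harms at 48 per arm even with perfect ascertainment. That is correct: 0/48 leaves rates up to 7.4% open, and one or two events do not separate the arms. A reader might infer that one missed event would change the safety conclusion; it would change the count only.

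A third tempting inference is that under-counting favours the arm with more polyps removed, because it has more resection sites. This is plausible, but the documents give no removal rate by arm, no risk per resection and no delayed-event rate. It remains conjecture.

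**Conclusion.** The concern holds in a limited form. The endpoint has no stated window or source, and nothing in the protocol provides for systematically finding perforation or transfused bleeding after the procedure day. Each arm's rate may therefore be understated, and any later events noticed incidentally would come from unequal observation times. This rests on the text and on the general premise that such complications can appear after discharge.

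The size is modest. One missed event moves an arm from 0/48 (upper limit 7.4%) to 1/48 (upper limit 11.1%), which changes the description but not a between-arm inference. The expected number of missed events, and the direction and size of any between-arm bias, cannot be derived from the documents. The primary endpoint, sample size and randomisation are unaffected. The change is still worth making: the endpoint will be purely descriptive, so its value depends on complete and equal ascertainment.

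**What to change.** Define the endpoint as major complications from the procedure through one fixed day, the same for every patient. Day 28 would match the existing 4-week period; day 30 would also serve, with the timeline text amended. In either case, reword the record-access sentence so that the look-up falls on or after the chosen day, because it currently sets only a latest time.

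At that look-up, abstract perforation, transfused bleeding, and any unplanned return visit or admission alongside pathology. Add complications to the data list in Procedures Involved so that it agrees with the privacy section. Report same-day and later events separately by arm, as counts with exact intervals and without a claim of equivalence. If only same-day events are intended, label the endpoint accordingly.

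The cost is a few extra fields in a chart access already planned for all 144 patients, with no added patient contact. The stated purpose of record access becomes wider, which may also require a change to the consent text. De-identification has to come after the look-up rather than immediately after procedure-day data collection. Events treated at other hospitals would still be missed, and the report should say so.

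### Randomised patients may be withdrawn on events of the study colonoscopy or at open discretion, with no visible rule keeping them in the analysis; cecal intubation rate is most exposed, adenoma detection rate less so

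*Combined protocol and SAP*

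**What the plan says.** The investigator-led routes are all in the combined protocol under Withdrawal of Subjects:

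- **Open discretion.** "A patient may be withdrawn from the research at the discretion of the endoscopist or PI". No criteria and no time limit are attached.
- **Findings of the procedure.** "The PI may withdraw a subject if there is a clinical suspicion for hereditary polyposis syndrome", or a "new case of inflammatory bowel disease (IBD) based on the colonoscopy".
- **Scope switch.** Where a pediatric colonoscope replaces the regular one, "In these cases, subjects may be withdrawn from the study". The section links this to "difficult anatomy or post-surgical anatomy preventing completion of the procedure using a standard colonoscope".

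Patients may also withdraw themselves, during or after the procedure. For none of these routes does the section say whether data already collected are kept, whether the patient is still counted in the assigned arm, or whether the patient is replaced.

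The analysis plan is a few sentences under Data Management and Confidentiality: "The data collected will be analyzed using one way ANOVA", a sample-size statement ending in the aim to "enroll 48 subjects into each arm", and a futility look after 6 months. No analysis population is named. Study Endpoints makes adenoma detection rate (ADR) primary and lists cecal intubation rate, without a definition, among six secondary endpoints. Adenoma status depends on a step after the procedure (Study Timelines): "Patient medical records will be accessed within 4 weeks of their colonoscopy for collection of final pathology report".

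**The concern.** Randomisation protects the comparison only while patients are counted where they were assigned. The findings route depends on what the study colonoscopy shows, and the switch route can depend on how it goes. The endoscopist, who may withdraw the patient, can presumably see which attachment is fitted. That is an inference: the protocol says single-blinded without saying who is blinded.

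For cecal intubation rate, the reason for a switch can overlap with failure to complete using the assigned method. Dropping switched patients could then remove failures from both numerator and denominator.

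For ADR, the main route is the discretion clause, which could be used before or after pathology is known. The direction is open: dropping adenoma-positive patients lowers an arm's rate, while dropping patients with a limited examination and no adenoma raises it.

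**Working it through.** **Inputs.** The protocol gives 48 patients per arm (Data Management and Confidentiality); 3 × 48 = 144 agrees with Number of Subjects. It gives no withdrawal rate, switch rate, ADR or cecal intubation rate, so there is no plan figure to reproduce on this point. Every count below other than 48 is an assumption made to show what dropping patients would do.

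**Formula.** With x patients having the outcome among n, and d dropped of whom d₊ had the outcome, the analysed rate is (x − d₊)/(n − d).

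**Cecal intubation rate.** Assume 2 switches in one arm and 6 in another, with every unswitched patient reaching the cecum.

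| How a switch counts | Who is dropped | Rates | Difference (points) |
|---|---|---|---|
| As failure | Nobody | 46/48 vs 42/48 (95.8% vs 87.5%) | 8.3 |
| As failure | Half of switched | 46/47 vs 42/45 (97.9% vs 93.3%) | 4.5 |
| As failure | All switched | 46/46 vs 42/42 | 0 |
| Any scope; half of switched reach cecum | Nobody | 47/48 vs 45/48 | 4.2 |
| Any scope; half of switched reach cecum | All switched | 46/46 vs 42/42 | 0 |
| Any scope; all switched reach cecum | Nobody, or all switched | 100% vs 100% | 0 either way |

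With 1 versus 3 switches counted as failures, the full difference is 47/48 − 45/48 = 4.2 points, and again 0 if all are dropped. The last row of the table shows that the problem vanishes under one reading of the endpoint, which is why its definition matters.

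**ADR, one arm of 48, nobody lost elsewhere.**

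| Full arm | 3 positives dropped | 3 negatives dropped |
|---|---|---|
| 10/48 = 20.8% | 7/45 = 15.6% (−5.3) | 10/45 = 22.2% (+1.4) |
| 20/48 = 41.7% | 17/45 = 37.8% (−3.9) | 20/45 = 44.4% (+2.8) |
| 24/48 = 50.0% | 21/45 = 46.7% (−3.3) | 24/45 = 53.3% (+3.3) |

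Dropping a single patient moves the rate by −1.7 to −1.1 points (a positive) or +0.4 to +1.1 points (a negative) over the same range.

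**ADR, equal removal from two arms.** The full difference is 30/48 − 20/48 = 20.8 points. With 1 positive dropped from each arm it is 29/47 − 19/47 = 21.3; with 3 from each, 27/45 − 17/45 = 22.2. Balanced removal does little.

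**The case against.** The best defence is that withdrawal from the research need not mean deletion. The clauses are permissive, nothing orders data to be discarded, and nothing prevents the investigators from analysing everyone as assigned. The consent form is not in the available text and may say what happens to data after withdrawal. These points stand, so the finding is a missing rule, not a stated exclusion. A consent form would not normally define the analysis population, so that gap remains.

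Second, unequal withdrawal is assumed. Difficult or post-surgical anatomy is a patient characteristic that randomisation should balance in expectation, and no section says an attachment changes how often the scope is switched. Histories are reviewed before the procedure (Recruitment Methods), and the timing of randomisation relative to scope choice is not given, so some of these cases may be known before assignment. This also stands; it limits the counts above to illustrations.

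Third, suspected polyposis and new inflammatory bowel disease resemble the exclusion criteria, and removing patients found late to be ineligible is a debatable choice rather than a plain error. Agreed, which is why that analysis belongs among the sensitivity analyses. The difference is that the exclusion criteria are applied before the procedure, while this clause acts on its findings.

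A reader might infer more than the text supports in two places:

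- That adenoma status would be unrecoverable for withdrawn patients because data are de-identified. The privacy section places de-identification after data collection, and its list of data includes the types of polyp removed. The pathology look-up is not restricted to patients who remain in the study.
- That the cecal comparison could change sign. That needs switched patients dropped in one arm and kept in another, and nothing in the protocol suggests such handling.

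**Conclusion.** The concern holds as a cheap improvement, with medium confidence. The protocol permits withdrawal of randomised patients on events linked to outcome, and no visible text keeps them in the analysis in their assigned arm. Cecal intubation rate is the most exposed endpoint, because the switch trigger can overlap with failure to complete. In the assumed case of 2 versus 6 switches counted as failures, 8.3 points can shrink to 0. ADR is less exposed: suspected polyposis is probably rare and would be adenoma-positive in any arm, so the risk lies mainly in the discretion clause. Losing 3 positives from an assumed 20/48 costs 3.9 points.

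Material bias requires that withdrawn patients are actually dropped, and that withdrawal is related to outcome and differs by arm. The documents establish none of these and give no rates, so size and direction are unknown. It would be wrong to conclude that the primary result will be biased, or biased in favour of a particular device.

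**What to change.** Add to the protocol:

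1. The primary analysis includes all randomised patients in whom colonoscopy is started, in their assigned arm, with adenoma status counted as found. Those randomised but never started are reported by arm.
2. Pathology is still collected for patients withdrawn by the endoscopist or PI, unless consent for data use is withdrawn. The consent form should be checked for agreement with this.
3. The timing of randomisation relative to scope choice is stated.
4. How a scope switch or incomplete examination counts for cecal intubation rate is fixed in advance. One option is completion with the assigned method, with completion by any scope also reported.
5. Withdrawals are reported by arm and reason.
6. The analysis excluding withdrawn or late-found ineligible patients is a sensitivity analysis.

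**Cost.** Protocol wording, and consent wording if needed; no extra patients or procedures. Polyp and histopathology data are already collected in routine care (Procedures Involved). That statement does not cover completion by scope type, so a little extra recording is needed. The statistical price is slight dilution of the contrast, from patients not completed with the assigned method and a few found late to be ineligible. Clinical decisions about changing scope are untouched.
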